### Study Intervention

Active study agents: Naloxone

Blinding/labeling/preparation of agents: No blinding is required in this study. The study drug will be prepared, unit dose labelled, and patient labelled according to institutional protocols.

Storage: Secured at room temperature in the central pharmacy then dispensed as a patient specific supply and stored at room temperature the automated dispensing cabinet. No more than a 24 hour supply will be dispensed at any given time.

Administration: 4 mg of a 1 mg/ml oral solution administered enterally (oral, nasogastric, orogastric, gastrostomy, or jejunostomy) every 8 hours for 48 hours

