**I. Analysis Plan**

Power Analysis

Power estimates for this study were based on prior work by Lee et al. In their study, patients were randomly assigned to receive morphine with naloxone or morphine without naloxone. They found that those who received naloxone had a shorter time to first postoperative passage of flatus ( $M = 51.9$ hr,  $SD = 16.6$ hr) versus control ( $M = 87.0$ hr,  $SD = 19.5$ hr). Similarly, the authors found that time to first feces was faster in the naloxone cohort ( $M = 95.3$ hr,  $SD = 25.0$ hr) than control group ( $M = 132.9$ hr,  $SD = 29.4$ hr). However, their study duration was exceedingly long with a maximum duration of approximately 160-180 hours. One goal of this study is to estimate the effect of naloxone on time to first feces within the first 120 hours (5 days) following treatment. In this study, patients who require a second intervention or who do not experience flatus or feces by Day 5 will be censored.

The null hypothesis is that the bowel movement (BM) rate is identical in the two groups (control and naloxone). Power is computed to reject this null hypothesis. Computation of power is based on a hazard ratio of 1.508. Specifically, it assumes instantaneous BM rates of 0.160 for the control group versus 0.241 for the naloxone group. This is equivalent to a median time of no BM of 4.34 days for the control group versus 2.879 days for the naloxone group. At 5 days, it is hypothesized that 45% of the control cohort versus 30% of the naloxone cohort will require a second intervention because they have not experienced a BM.

With a total of 150 patients entered into the naloxone group and a total of 150 historical controls, the study will have power of 80.1% to yield a statistically significant result. The

criterion for significance (alpha) is set at 0.050, and the test will be 2-tailed meaning an effect in either direction will be interpreted.

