#### Analysis Plan

Two different approaches will be used for the primary aim. First, a paired *t*-test will be used to estimate the mean difference in hours to first feces between the active cohort and historical control cohort. For this analysis, the origin of time for both groups is start of surgery. If necessary, a Wilcoxon signed ranks test will be used to compare the two distributions.

A second approach will compare the instantaneous rates of bowel movements between the active and control cohorts using a Frailty survival model that allows for clustering of patients within their matched strata. In this analysis, control patients who required treatment for ileus will be censored at the time of such treatment, and active patients who require an additional treatment beyond receipt of naloxone will be censored at the time of such treatment. All patients who do not achieve BM by 120 hours will also be censored. Hours to first feces for both groups will be start of surgery. While we assume there is no immortal time bias between start of surgery and receipt of naloxone for the active cohort, a conditional landmark method may be used to account for the amount of hours between surgery and receipt of naloxone. The proportional hazards assumption for all predictors will be tested using Martingale residuals as described by Lin, Wei, and Ying.

Regarding the secondary aims, a linear mixed effects model will be used to compare LOS between the two groups. A generalized linear mixed effects model will be used to compare the two groups on all other secondary outcomes. In these models, random intercepts will be allowed for each case-control matched strata in order to account for the correlation between cases and controls based on age, gender, Charleston co-morbidity index, and operation time under anesthesia.

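### The hazard comparison censors patients at rescue treatment and never checks it; if rescue tracks a poor outlook for bowel movement and practice differs between cohorts, the hazard ratio is biased

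*Combined protocol and SAP*

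**What the plan says.** The Analysis Plan gives two approaches to the primary aim. The second is a frailty survival model, clustered on matched strata, that compares BM rates up to 120 hours. Its censoring rule is worded differently for each cohort:

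- Historical cohort: "control patients who required treatment for ileus will be censored at the time of such treatment".
- Naloxone cohort: "active patients who require an additional treatment beyond receipt of naloxone will be censored at the time of such treatment".
- Both cohorts: "All patients who do not achieve BM by 120 hours will also be censored".

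The Power Analysis has a third wording for both cohorts together: "patients who require a second intervention or who do not experience flatus or feces by Day 5 will be censored". It also gives the reason for the second intervention, expecting that at 5 days "45% of the control cohort versus 30% of the naloxone cohort will require a second intervention because they have not experienced a BM".

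Four other features matter:

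- The controls come from the previous 3 years (Screening procedures).
- The trial is open: "No blinding is required in this study" (Study Intervention).
- Bowel care follows the usual order sets, and no time or trigger for further treatment is fixed (Study Assessments and Activities).
- Ileus is diagnosed from examination and X-ray together (Study Design).

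**The concern.** A censored patient is treated as having, from that moment, the same chance of a BM as comparable patients who stay under observation. That is reasonable when follow-up ends at 120 hours. It is doubtful when the patient leaves because a clinician examined them, perhaps looked at an X-ray, and judged that the bowel was not recovering. Removing such patients raises the apparent BM rate of those left.

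If this happened equally in both cohorts, it would largely cancel. Here one cohort is watched prospectively by staff who know the treatment, and the other had ordinary past care. More frequent removal of poor-outlook patients from the naloxone cohort would favour naloxone with no drug effect. More frequent removal from the controls would hide a real effect.

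Nothing planned would reveal this. The landmark option addresses the delay from surgery to naloxone. The matched-stratum frailty term addresses correlation between matched patients, not selection of who is censored. Matching uses age, gender, co-morbidity, complexity and duration of surgery, not postoperative bowel signs. The plan does not say how rescued patients enter the paired *t*-test, so that test cannot be counted as a check.

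**Working it through.** **1. The plan's own figure.** Inputs from the Power Analysis: BM rates of 0.160 and 0.241 per day, 150 per group, 5 days, two-sided alpha 0.05, and "Computation of power is based on a hazard ratio of 1.508".

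- No BM at day 5: exp(−0.160 × 5) = exp(−0.8) = 0.449; exp(−0.241 × 5) = exp(−1.205) = 0.300.
- Expected events: 150 × (1 − 0.449) + 150 × (1 − 0.300) = 82.6 + 105.0 = 187.6.
- Schoenfeld power: Φ(√(187.6/4) × ln 1.508 − 1.96) = Φ(2.814 − 1.960) = 80.3%. With 0.241/0.160 = 1.506 it is 80.1%.

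The stated 80.1% reproduces. The 45% and 30% are simply the proportions without a BM at day 5, so the power model contains no rescue before then. As an outer bound, if everyone without a BM were censored at 4 days, events would fall to 164 and power to 75%; at 3 days, to 134 and 66%.

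**2. Set-up for the bias check.** The true hazard ratio (HR) is 1 throughout, so any departure is bias. Assumed, because the documents give no such figures: a BM rate of 0.2 per day, patient outlook varying by a gamma frailty of variance 0, 0.5 or 1.0, and the rescue rates shown. Follow-up is cut at 5 days. The HR comes from 400,000 patients per cohort and the rejection rate from 1,500 trials of 150 + 150. The Monte Carlo standard error at 5% is √(0.05 × 0.95/1500) = 0.6 percentage points. The Cox fit is unmatched and has no frailty term.

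**3. Rescue depends only on still having no BM; practice differs.** The cases were a fixed time of 4 against 3 days, 0.05 against 0.20 per day, and a 3-day trigger followed by 0.1 against 1.0 per day. HR 0.99 to 1.00, rejection 4.5 to 6.3%, with or without frailty. No material bias.

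**4. Rescue tracks outlook; practice is the same** (0.15 per day in both). HR 1.00, rejection about 5%. No bias.

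**5. Rescue tracks outlook and practice differs** (control rate against naloxone rate, per day). In the moderate link, rescue is 1.6 times the base rate for below-median outlook and 0.4 times otherwise. In the strong link, it is inversely proportional to the frailty.

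| Scenario | Frailty variance 0.5: HR (rejection) | Frailty variance 1.0: HR (rejection) |
|---|---|---|
| Moderate link, 0.05 vs 0.20 | 1.09 (8.2%) | 1.11 (8.0%) |
| Moderate link, 0.20 vs 0.05 | 0.92 (8.2%) | 0.89 (9.3%) |
| Strong link, 0.05 vs 0.20 | 1.13 (11.4%) | 1.20 (16.1%) |
| Common 3-day trigger, then moderate link, 0.1 vs 1.0 | 1.04 (4.9%) | 1.05 (6.3%) |

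Bias needs both conditions together. A common trigger reduces it but does not wholly remove it.

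**6. The candidate replacements.** Null rate 0.160 per day in both cohorts, rescue from day 2 at 0.1 (control) against 0.4 (naloxone) per day, unrelated to outlook.

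- Censoring at rescue, as planned: HR about 1.00, rejection about 5%.
- Rescued patients kept as having no BM to 120 hours: HR about 0.84, rejection 17 to 20%. With the rates reversed, HR about 1.19 and 19%.
- All BMs counted regardless of rescue: HR 1.00, rejection 4 to 5%, if rescue does not change BM time. If rescue doubles the BM rate, HR is about 1.1 (by symmetry about 1/1.1 = 0.9 with the rates reversed).

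**The case against.** The strongest reply is that everyone still at risk has had no BM. Treating someone because no BM has occurred therefore uses only the history already observed, and censoring on that history alone is independent censoring. This stands, and step 3 confirms it. A reader might infer that any difference in rescue practice creates a false hazard ratio. The documents do not support that: a link between rescue and outlook is also needed, and the plan neither states nor excludes one.

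A reader might also infer a much larger bias. If rescue on days 2 to 5 is given only to patients who will in fact have no BM by day 5, to 50% of them among controls and 100% in the naloxone cohort, the null HR is 1.23 with 26% false positives. No clinician can know on day 2 who those patients are, so this is a near-extreme case and not a forecast.

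Nor does the plan discard the 45% and 30% that its hypothesis counts. Those patients have no BM at day 5 and are censored there administratively; anyone rescued earlier contributes time at risk until rescue.

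It may be added that medication escalations are already a secondary outcome. That helps with data, but the outcome is not tied to the censoring rule and does not test it. The reply leaves the conditional concern intact: ileus treatment rests on clinical and X-ray findings, the cohorts are managed in different settings, and the plan offers no check.

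**Conclusion.** The concern holds conditionally. Censoring at rescue is valid if rescue depends only on time without a BM, or if it tracks outlook equally in both cohorts. If it tracks outlook and practice differs, the hazard ratio can be biased in either direction: roughly 0.9 to 1.2 with no true effect under assumed 4-fold differences, with 8 to 16% rejection instead of 5%, and about 1.05 with a common 3-day trigger. Against the planned hazard ratio of 1.508, bias of that size would not manufacture the whole hypothesised effect, but it could distort a modest one.

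These sizes rest on assumed BM rates, frailty variances and rescue rates, and on an unmatched Cox fit in place of the planned frailty model. What rests on the documents alone is that the censoring rule has three wordings, two of which differ by cohort, and that no planned analysis tests whether censoring at rescue is independent.

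**What to change.** 1. Reconcile the censoring wording in the Power Analysis and the Analysis Plan, so that it is clear which event ends follow-up in each cohort.
2. Keep the censored frailty model. Pre-specify beside it the same comparison of time to first BM to 120 hours with every first BM counted, whether or not rescue came first.
3. Add a sensitivity analysis with rescue as a competing event.
4. Report the number and timing of rescue treatments by cohort.
5. State in advance that the hazard comparison supports a naloxone effect only if the censored and all-BM results agree in direction and broadly in size.

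Keeping rescued patients as having no BM to 120 hours should not become the main analysis: it is biased whenever rescue frequency differs between cohorts, as step 6 shows.

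The cost is SAP text, extra model runs, and recording of BMs after rescue. Daily BMs and laxative escalations are already outcomes, so the main practical question is whether the historical charts time these events well enough. The all-BM version has its own weakness, since it includes any effect of the rescue treatment itself. No one version should stand alone.

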### Study Assessments and Activities

All patients will undergo the scheduled operation per routine. Post operatively, all usual medications for pain control and bowel movements will be ordered according to institutionally approved and reviewed post-operative order sets. All home medications will also be reconciled and restarted as deemed clinically appropriate by the interdisciplinary care team. Oral naloxone 4 mg enterally every 8 hours will be initiated on post-operative day 1 at 0900. Study drug will be discontinued as described in the study protocol, after 48 hours, or upon discharge whichever is sooner.

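### The stated goal and the 80.1% power rest on a full 5 days of naloxone effect, but the survival analysis stops 120 hours after the start of surgery, about 94 to 104 hours after the first dose

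*Combined protocol and SAP*

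**What the plan says.** The Power Analysis gives as one goal to "estimate the effect of naloxone on time to first feces within the first 120 hours (5 days) following treatment". It then says that "patients who require a second intervention or who do not experience flatus or feces by Day 5 will be censored", without naming the origin of Day 5. The power of 80.1% uses 150 patients per group, a two-sided alpha of 0.05, daily BM rates of 0.160 (control) and 0.241 (naloxone), a hazard ratio of 1.508, and 45% versus 30% without a BM at 5 days.

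The Analysis Plan has two primary approaches. For the paired t-test, "For this analysis, the origin of time for both groups is start of surgery", and no 120-hour limit is stated. The frailty model has the limit and is also counted from the operation: "All patients who do not achieve BM by 120 hours will also be censored. Hours to first feces for both groups will be start of". The same paragraph recognises the interval before dosing and says that "a conditional landmark method may be used to account for the amount of hours between surgery and receipt of naloxone". It gives neither a landmark time nor a horizon.

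Study Assessments and Activities fixes the start of drug: "Oral naloxone 4 mg enterally every 8 hours will be initiated on post-operative day 1 at 0900". Under Study Intervention, dosing lasts 48 hours.

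**The concern.** The two 120-hour windows start from different points. On the natural reading, treatment in a sentence about the naloxone effect means naloxone, and the Analysis Plan itself distinguishes surgery from receipt of naloxone. A first BM 130 hours after surgery, with the first dose at 24 hours, comes 106 hours after that dose. It falls inside the stated goal but is censored in the frailty model.

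Two things are at stake. The survival analysis does not estimate the effect over the period that the plan names. And the stated power credits naloxone with 5 days of effect, whereas on a surgery clock the first part of those 5 days precedes any dose.

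**Working it through.** **Inputs.** From the Power Analysis: 150 + 150 patients; 45% and 30% without a BM at 5 days; hazard ratio 1.508; two-sided alpha 0.05. From the Analysis Plan: censoring at 120 hours from start of surgery. Assumed: surgery starts between 17:00 and 07:00 on the previous day, a gap of 16 to 26 hours, with 24 hours as the central case; no naloxone effect before the first dose; constant rates; no early rescue.

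**1. The plan's figure.** Rates are −ln(0.45)/5 = 0.1597 and −ln(0.30)/5 = 0.2408 per day, ratio 1.508. Expected events are 150 × 0.55 + 150 × 0.70 = 187.5. Schoenfeld power is Φ(ln 1.508 × √(187.5/4) − 1.96) = Φ(2.81 − 1.96) = 80.3%. The stated 80.1% therefore reproduces, with the hazard ratio acting over all 5 days.

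**2. Post-dose window.** 120 − 26 = 94 hours; 120 − 24 = 96 hours; 120 − 16 = 104 hours.

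**3. Patients without a BM at the first dose (24-hour gap).** At risk per group: 150 × exp(−0.1597) = 127.9.
- To 120 hours from surgery (4 days after dosing): 127.9 × (1 − e^(−0.1597×4)) + 127.9 × (1 − e^(−0.2408×4)) = 60.4 + 79.1, or 139.4 events before rounding. Power is Φ(2.43 − 1.96) = 68%.
- To 120 hours after the first dose: 70.3 + 89.5 = 159.8 events. Power is Φ(2.60 − 1.96) = 74%.

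**4. All patients, clock from surgery (24-hour gap).** About 300 × (1 − e^(−0.1597)) = 44 events occur before dosing, when the hazard ratio is 1 by assumption. Power below comes from integrating the log-rank statistic over time.
- To 120 hours: about 184 events, average hazard ratio 1.364. Check: ln 1.364 × √(183.8/4) = 2.10, power 56%. Over gaps of 16 to 26 hours, power runs from 64% down to 54%.
- To 144 hours: about 204 events, average hazard ratio 1.378. Check: ln 1.378 × √(204.2/4) = 2.29, power 63%.

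A log-rank simulation (4,000 runs) agrees: 67% and 75% for step 3, 56% and 62% for step 4.

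**5. Source of the shortfall.** From surgery, power falls from 80% to 63% because of pre-dose time (17 points), and from 63% to 56% because of the earlier cut-off (7 points). Among patients at risk at the first dose, the two parts are close to equal: 80.3% to 73.8%, then 73.8% to 67.9%.

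**6. Events between 120 and 144 hours.** Controls without a BM go from 45.0% to 38.4%, and naloxone patients from 32.5% to 25.6%. That is about 20 of 300 patients (159.8 − 139.4 = 20.4).

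**7. If there is no effect after 120 hours.** Dosing ends by about 24 + 48 = 72 hours after surgery, so the added day lies 48 to 72 hours after dosing ends. With a hazard ratio of 1 in that day, extending to 144 hours lowers power from 68% to 63% (step 3) and from 56% to 52% (step 4).

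**The case against.** The strongest reply is that the conflict rests on one undefined word in a narrative sentence. Historical controls receive no naloxone, so time after treatment has no meaning for them unless a reference time is named, and treatment could loosely mean the operation. The operative section names start of surgery for both approaches. This is a fair reading, and it could remove the wording conflict. It does not rescue the power, because the 80.1% would then assume a naloxone effect from the start of surgery, before any dose.

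Several stronger inferences are open to a reader, and the reply is right to resist them:
- That events after 120 hours are lost to the primary analysis. The limit is stated for the frailty model only.
- That the hazard ratio is biased. The cut-off falls at the same time in both groups, and censored patients still contribute 120 hours at risk. Under proportional hazards the cost is precision.
- That 80.1% is an arithmetic error. It follows from its inputs. At constant rates from surgery, 144 hours would give 207.2 events and 84.1%, so the cut-off takes nothing from the stated figure as computed.
- That a landmark analysis would keep the surgery-based cut-off. The plan leaves that horizon open.
- That follow-up must be lengthened. The plan expects patients without a BM at 5 days to need a second intervention, and it censors at such treatment. If Day 5 runs from surgery, the added day may yield few events; discharge would reduce them further. Step 7 shows that the gain can also reverse.

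**Conclusion.** The point holds as a mismatch between goal, analysis window and power. With treatment read as naloxone and a gap of 16 to 26 hours, the survival analysis covers about 94 to 104 hours after the first dose against a stated 120. With a 24-hour gap, the plan's rates, no effect before dosing and no early rescue, power is about 56% from surgery (54% to 64% over the range of gaps) and about 68% among patients without a BM at the first dose. These figures describe the frailty comparison approximated by a log-rank test; they do not address the paired t-test. Pre-dose time accounts for most of the shortfall in the analysis from surgery, so moving only the end of the window would not restore 80%.

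It would be tempting to conclude that the 120-hour cut-off is wrong and that 144 hours should replace it. The documents do not support that. A planned cut-off two days after dosing ends is defensible, and the sign of any gain depends on whether the effect persists.

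**What to change.** State one origin and one horizon for both cohorts, and use them in the Power Analysis, in the frailty model and in any landmark analysis. For controls, take 0900 on post-operative day 1 as the reference time that matches the first dose. If the landmark method is used, give its time and horizon, and say that only patients without a BM at that time enter.

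If 120 hours from surgery is kept, change the goal to the effect over about 96 hours after the first dose, with the actual gap stated, and restate the power for that window with no effect before dosing.

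Extending follow-up to 120 hours after the reference time is an option. It adds about 20 events and about 6 points of power only if the effect persists after dosing ends and patients are still observed without rescue. It lowers power if there is no effect after 120 hours. If chosen, those assumptions should be stated.

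The cost is SAP wording and one power calculation. The optional extension adds about one day of bowel-record abstraction for patients still in hospital. Neither change by itself adds patients or alters care; the restated power may lead the sponsor to reconsider whether 150 per group is enough.

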### **I. Study Design**

This is a prospective, historically controlled observational trial of enteral naloxone use in patients admitted for spinal fusion surgery and receiving opioids for pain management.

Primary outcome: Time to first bowel movement (hours)

Secondary outcomes:

- Hospital length of stay
- Incidence of post-operative ileus. Post-operative ileus will be diagnosed through a combination of clinical exam and radiographic (X-ray) findings
- incidence of post-operative constipation (defined as 3 days without a bowel movement)
- average numerical pain scale (Adult Nonverbal Pain scale or Visual Analog Scale) on post-operative days 0, 1, 2, and 3
- average daily opioid requirement on post-operative days 0, 1, 2 and 3 (morphine equivalents)
- number of naloxone doses administered
- average number of daily bowel movements,
- number of medication escalations required (defined as use of an as needed laxative medication or addition of a new order for a laxative medication)
- Incidence of adverse effects
- Incidence of study drug discontinuation

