### Screening procedures

Patients will be screened at the pre-operative clinic visit based on the inclusion and exclusion criteria.

Historical controls will be identified by a report of patients undergoing spinal fusion procedures

identified via ICD9 codes in the previous 3 years. ICD-9 codes include a short fusion surgery (81.06, 81.62) with 3 or fewer vertebral body segments, long fusion surgery (81.63, 81.64), more than 4 vertebral segments, anterior approaches (81.06) and posterior approaches (81.07) in the thoracic and lumbar spine. The historical controls will be matched to active participants based on age, gender, Charleston co-morbidity index, complexity of surgery, and duration of surgery.

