### **III. Safety Monitoring Plan**

Definition of adverse events, serious adverse events

Adverse event: Any reported or observed event that is not part of the usual post-operative clinical course.

Serious adverse event: Any event that requires discontinuation of the study drug

Any serious adverse events will be reported immediately to the IRB. All identified adverse events will be reported in the final analysis of this study. Upon completion of data collection, all adverse events will be evaluated by study personnel and adjudicated for their relation to study drug.

What procedures will be used to monitor subject safety

Patients will be monitored for adverse effects via routine vital signs, pain, and neurological assessment every 1 – 4 hours and evaluation for emesis, bowel movements, and diaphoresis. These evaluations do not represent an additional burden to the patient since they are a part of routine post-operative care.

Protected health information and data security

All protected health information associated with the historical cohort will be stored in a password protected Microsoft Excel file on the SSOM Research secured drive. De-identified patient information will be entered into a RedCap database for data collection. All signed consent forms will be collected and securely kept in the patients' medical record through EPIC.

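### The between-cohort model covers naloxone doses and drug discontinuation, which untreated controls cannot have, and adverse effects, for which no common ascertainment is set

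*Combined protocol and SAP*

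**What the plan says.** The Study Design section describes a "prospective, historically controlled observational trial of enteral naloxone use". Its secondary outcomes include "number of naloxone doses administered", "Incidence of adverse effects" and "Incidence of study drug discontinuation", as well as pain scores and daily opioid requirement on post-operative days 0 to 3.

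The Analysis Plan gives length of stay a linear mixed model and then states: "A generalized linear mixed effects model will be used to compare the two groups on all other secondary outcomes". A random intercept for each matched stratum is specified. No distribution or link is named, and no outcome is set aside as descriptive.

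On the control cohort, Screening procedures says: "Historical controls will be identified by a report of patients undergoing spinal fusion procedures". The report uses ICD-9 codes and covers the previous three years.

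The Safety Monitoring Plan defines an adverse event as "Any reported or observed event that is not part of the usual post-operative clinical course" and a serious adverse event as "Any event that requires discontinuation of the study drug". Study personnel judge each adverse event's relation to study drug once data collection is complete. The same section describes the monitoring as part of ordinary post-operative care. The stopping criteria under Toxicities and guidelines for adjustments are read in the hour after a study dose. Study Intervention states that there is no blinding.

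**The concern.** There are two separate problems.

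First, doses and discontinuation describe exposure to the study drug. A patient who never received it has no dose count other than zero and cannot stop it. A between-group model of either outcome answers no question.

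Second, adverse effects can occur in both cohorts, but the plan does not say how they will be found in the controls. One cohort is observed prospectively by staff who know that the patient is on naloxone; the other is reached through old records. Three parts of the safety apparatus need a study drug in order to apply: the serious adverse event definition, the causality judgement and the one-hour criteria. If control events are recorded less completely, the model will show an excess on naloxone that the drug did not cause.

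Safety is half of the stated study aim, so a misleading contrast here would matter even though it is secondary.

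**Working it through.** **The plan's own figure.** The plan states no figure for any safety outcome. Its only power figure is for the primary outcome, and it reproduces.
- Inputs (Power Analysis): rates of 0.160 and 0.241 per day, 5 days, 150 per group, hazard ratio 1.508, two-sided alpha 0.05.
- Expected events: 150(1 − e^(−0.800)) + 150(1 − e^(−1.205)) = 82.6 + 105.0 ≈ 187.6.
- Schoenfeld: Φ(√187.6 × ln 1.508 / 2 − 1.96) = Φ(2.81 − 1.96) ≈ 80.3%, against 80.1% stated.

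Nothing below changes it.

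**Discontinuation.** Let a be the intercept and b the group effect on the logit scale. Every control outcome is 0. Hold a + b fixed and let a fall. The naloxone patients' contributions do not move, and each control's contribution rises towards 1. The likelihood therefore increases without limit in b, and no finite maximum exists. A random stratum intercept does not alter this, because the argument holds at every value of that intercept. This is quasi-complete separation: the controls are all zeros, while the naloxone cohort contains both outcomes.

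A numerical check used the fixed-effect part only, with 0 of 150 controls and an assumed 5 of 150 naloxone patients discontinuing. The coefficient was 8.2, 23.2 and 33.8 after 10, 25 and 50 iterations, and its standard error grew from 16 to over 5 million.

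**Doses.** Dosing every 8 hours for 48 hours gives 48/8 = 6 doses (7 if both ends are counted). With 0 against 6 doses, a Poisson log rate ratio diverges in the same way: 11.4, 26.4, 39.3. An identity link gives a finite difference of about 6 − 0 = 6, which is simply the dosing schedule.

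**Adverse effects.** The documents give neither an incidence nor a capture rate, so these inputs are assumptions. Take the same true rate p in both cohorts, full capture on naloxone and a captured fraction c in controls. The spurious odds ratio is [p/(1 − p)] / [cp/(1 − cp)]. At p = 0.10:
- c = 0.9: (0.10/0.90)/(0.09/0.91) = 1.12
- c = 0.8: (0.10/0.90)/(0.08/0.92) = 1.28
- c = 0.5: (0.10/0.90)/(0.05/0.95) = 2.11

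The next table gives the chance of a significant false excess on naloxone with 150 per group, treated as independent samples. The nominal chance in that direction is 2.5%. Each range runs from p = 10% to p = 40%.

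| Control capture | Chance of false excess |
|---|---|
| 90% | 5–11% |
| 80% | 9–30% |
| 70% | 15–59% |
| 50% | 38–97% |

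**The case against.** The strongest reply is that the plan is less asymmetric than it looks.
- There is one adverse event definition, and it names no cohort. Only the serious adverse event definition and the causality judgement depend on the drug.
- The listed outcome is adverse effects. The toxicity section uses that term for a set of physical signs, and the plan says these are observed in routine care. Such signs could be in the controls' charts as well.
- Nothing in the Analysis Plan limits the modelled count to drug-related events, so the adjudication need not lower the control count.
- A comparison of doses with untreated patients is so plainly empty that it would mislead nobody.

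Much of this stands. A reader might infer that adverse events are defined differently in the two cohorts, that the comparison is biased against naloxone by construction, or that the whole safety comparison is invalid. The documents do not support these readings. The definition is common to both cohorts. Unequal capture is an inference from the design and is not stated. Pain scores and opioid requirement bear on loss of analgesia, the main hazard that the plan names, and can be compared in both cohorts.

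Routine monitoring does not close the gap, however. The plan sets no chart source, time window or abstraction rule for the controls, and unblinded staff decide what counts as outside the usual course. That the empty comparisons are obvious is a reason to correct one sentence, not to leave it.

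**Conclusion.** The concern holds in two parts of different strength.

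The comparisons of doses and discontinuation have no content as written. This follows from the text and needs no assumption about rates. It does assume that the dose outcome counts enteral study drug; the plan does not say whether naloxone given for another reason would count. The absence of a finite group effect is specific to a log or logit link, and the plan names no link.

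The adverse-effect comparison is at risk of ascertainment bias, which is not the same as shown to be biased. The size depends wholly on assumed capture. At a 10% true rate the spurious odds ratio runs from about 1.1 (90% capture) to 2.1 (50% capture), and the upper figure is the extreme of the values tried. Lower capture in the controls is the more plausible direction, but the documents do not establish it.

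**What to change.** In the Analysis Plan, replace the all-inclusive sentence with a list of the outcomes to be modelled, and then:

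1. Take the number of naloxone doses, study drug discontinuation, serious adverse events and drug-relatedness out of the between-group model. Report them for the naloxone cohort only: doses as a distribution, and proportions with exact confidence intervals.
2. Limit the between-cohort safety comparison to signs charted routinely in both cohorts (heart rate, respiratory rate, emesis, liquid stools), alongside the pain score and opioid requirement already planned.
3. Take these signs from the same chart fields in both cohorts, with one written abstraction rule and the same hours after surgery. Do not use a clock tied to a naloxone dose, which controls do not have.

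The cost is the SAP wording and one common abstraction form. The between-cohort comparison of adjudicated adverse events is given up. No extra patients are needed, and the sample size and alpha do not change.
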